### 8.3.6.2.3. Pulmonary Adverse Events

Pulmonary AEs including radiographic changes (eg, focal ground glass opacities and patchy infiltrates) indicative of drug-related pneumonitis have been observed in participants receiving anti-PD-1 therapies. These pulmonary AEs were either asymptomatic or associated with symptoms such as dyspnea, cough, or fever. The initial occurrence of pulmonary AEs may be as early as after a single dose of anti-PD-1 therapies or delayed after prolonged therapy. Early recognition and treatment of pneumonitis is critical to its management (refer to [Table 8](#)). Participants should be advised to seek medical evaluation promptly if they develop new-onset dyspnea, cough, or fever or if they have worsening of these baseline symptoms.

**Table 8: Management of Pulmonary Adverse Events**

| Grade            | Recommended Actions  |
|------------------|--|
| Grade 1   | Monitor for symptoms every 2-3 days; consider pulmonary and infectious-disease consult; re-image every 3 weeks
Worsening: treat as $\geq$ Grade 2  |
| Grade 2   | Monitor symptoms daily; re-image every 1-3 days; pulmonary and infectious-disease consultation; consider bronchoscopy and lung biopsy; consider hospitalization
Immediately: start 1.0 mg/kg/d methylprednisolone IV or oral equivalent; prophylactic antibiotics; discontinue nivolumab
Persistence for 2 weeks or worsening: treat as Grade 3-4
Improvement to <math>\leq</math> Grade 1 or baseline: taper steroids over at least 4 weeks |
| Grade 3-4 | Hospitalize; pulmonary and infectious-disease consult; consider bronchoscopy and lung biopsy
Immediately: 2-4 mg/kg/d methylprednisolone or IV equivalent; add prophylactic antibiotics; discontinue nivolumab
Persistence for 2 days or worsening: add immunosuppression (eg, infliximab, cyclophosphamide, IVIG, or mycophenolate mofetil)
Improvement to <math>\leq</math> Grade 2: taper steroids over at least 6 weeks                  |
| General   | Patients on IV steroids may be switched to an equivalent dose of oral corticosteroids (eg, prednisone) at start of tapering or earlier, once sustained clinical improvement is observed. The lower bioavailability of oral corticosteroids needs to be considered  |

### 8.3.6.2.4. Renal Adverse Events

Elevated creatinine and biopsy-confirmed tubulointerstitial nephritis and allergic nephritis have been infrequently observed following treatment with anti-PD-1 therapies. Investigators should monitor creatinine regularly.

If renal complications develop, participants should be closely monitored for disturbances in creatinine clearance. Additional investigations can be performed at the investigator's discretion. Participants must be treated as clinically appropriate.

In case of suspicion of immune-related renal events, please refer to [Table 9](#) for guidance.

**Table 9: Management of Renal Adverse Events**

| Grade     | Recommended Actions  |
|-----------|--|
| Grade 1   | Monitor creatinine weekly
Creatinine returns to baseline: continue monitoring per protocol
Creatinine increases: treat as Grade $\geq 2$   |
| Grade 2-3 | Monitor creatinine every $\leq 3$ days
Immediately: start 0.5-1.0 mg/kg/d methylprednisolone IV or oral equivalent; consider prophylactic antibiotics; consider renal biopsy; discontinue nivolumab
Improvement to <math>\leq</math>Grade 1: taper steroids over at least 4 weeks
Persistence <math>>7</math> days or worsening: treat as Grade 4 |
| Grade 4   | Monitor creatinine daily
Immediately: consult nephrologist; consider renal biopsy; start 1.0-2.0 mg/kg/d methylprednisolone IV or IV equivalent; add prophylactic antibiotics; discontinue nivolumab
Improvement to <math>\leq</math>Grade 1: taper steroids over at least 4 weeks   |
| General   | Participants on IV steroids may be switched to an equivalent dose of oral corticosteroids (eg, prednisone) at start of tapering or earlier, once sustained clinical improvement is observed. The lower bioavailability of oral corticosteroids needs to be considered.   |

### 8.3.6.2.5. Endocrinopathies

Endocrinopathies have been observed following treatment with anti-PD-1 therapies. The events have typically been identified through either routine periodic monitoring of specific laboratory tests (eg, TSH) or as part of a work-up for associated symptoms (eg, fatigue). Events may occur within weeks of beginning treatment, but also have been noted to occur after many months (while still on treatment). More than 1 endocrine organ may be involved (eg, hypophysitis [pituitary inflammation] may need to be evaluated at the time adrenal insufficiency or thyroid disorder is suspected). Participants should be advised to seek medical evaluation if they notice new-onset fatigue, lightheadedness, or difficulty with vision or if baseline fatigue worsens. Refer to [Table 10](#) for the management of immune-related endocrinopathies.

**Table 10: Management of Immune-Related Endocrinopathies**

| Grade                      | Recommended Actions   |
|----------------------------|---|
| Asymptomatic TSH elevation | TSH <math><0.5 \times</math>LLN or TSH <math>>2 \times</math>ULN or TSH <math>>ULN</math> in 2 subsequent measurements: include free T4 assessment prior/after subsequent cycles of study treatment; consider endocrinology consultation  |
| Symptomatic endocrinopathy | Assess endocrine function with appropriate laboratory testing; consider pituitary MRI scan
With abnormal lab and pituitary scan: 1.0–2.0 mg/kg/d methylprednisolone IV or oral equivalent; initiate appropriate hormone therapy; consider prophylactic antibiotics; discontinue nivolumab 
 
In hyperthyroidism, non-selective beta-blockers (eg, propranolol) are suggested as initial therapy.
 
In hypothyroidism, thyroid hormone replacement therapy, with levothyroxine or liothyronine, is indicated per standard of care.
 
 Clinical and laboratory improvement: taper steroids over at least 4 weeks; patients with adrenal insufficiency may need to continue steroids with mineralocorticoid component
Without abnormal lab and pituitary scan but symptoms persist: repeat laboratory assessments in $\leq 3$ weeks and MRI in 4 weeks |

| Grade  | Recommended Actions   |
|--|---|
| Suspicion of adrenal crisis (eg, severe dehydration, hypotension, shock out of proportion to current illness)  | Rule out sepsis
Immediately: initiate/stress dose of IV corticosteroids; fluids IV; consult endocrinologist; discontinue nivolumab
Adrenal crisis ruled out: treat as symptomatic endocrinopathy  |
| Type 1 diabetes mellitus (if new onset, including diabetic ketoacidosis [DKA]) or $\geq$ Grade 3 Hyperglycemia, if associated with ketosis (ketonuria) or metabolic acidosis (DKA) | For T1DM or Grade 3-4 Hyperglycemia: Insulin replacement therapy is recommended for Type I diabetes mellitus and for Grade 3-4 hyperglycemia associated with metabolic acidosis or ketonuria.
Evaluate patients with serum glucose and a metabolic panel, urine ketones, glycosylated hemoglobin, and C-peptide. |
| General  | Patients on IV steroids may be switched to an equivalent dose of oral corticosteroids (eg, prednisone) at start of tapering or earlier, once sustained clinical improvement is observed. The lower bioavailability of oral corticosteroids needs to be considered.  |

### 8.3.6.2.6. Rash

Nivolumab can cause immune-mediated rash or dermatitis, defined as requiring the use of steroids and no clear alternate etiology. Exfoliative dermatitis, including Stevens-Johnson Syndrome, toxic epidermal necrolysis (TEN), and drug rash with eosinophilia and systemic symptoms (DRESS) has occurred with PD-1/L-1 blocking antibodies.

Participants should be informed that they should contact their doctor immediately when they notice any generalized skin reaction. This skin reaction should be evaluated in the clinic the same day (if possible) or the next possible day.

All rash events should be captured in the AE section of the CRF. Separate Rash pages will be completed in case of a rash event.

Monitoring of the evolution and management of rash events will be performed as described in [Table 14](#) in Section 10.6, Appendix 6: Rash Management.

Digital pictures may be taken when considered appropriate at the discretion of the investigator and in accordance with local regulations; it is recommended to collect images in case of Grade 3 and 4 rash or other skin reactions. Digital pictures will only be taken and collected from participants who consent separately to this component of the study. If digital pictures are taken, they should be anonymized and provided to the sponsor.

When safety blood samples are drawn as per the rash management guidelines, these should be processed by the local laboratory. The following parameters will need to be tested: AST, ALT, sedimentation rate, complete blood cell count (including hemoglobin, hematocrit, red blood cell [RBC] count, white blood cell [WBC] count, differential count [neutrophils, lymphocytes, monocytes, eosinophils, and basophils], and platelet count), and creatinine. The values of the local laboratory assessments need to be transcribed in the CRF by the study site personnel.

The participant may be treated symptomatically until the rash resolves. Oral antihistamines (eg, cetirizine, levocetirizine) and/or topical corticosteroids may provide symptomatic relief, but effectiveness of these measures has not been established. JNJ-3989 and nivolumab should be discontinued in case of  $\geq$ Grade 3 rash. If systemic corticosteroids are required for treatment of rash, nivolumab must be permanently discontinued. If systemic corticosteroids exceeding 5 mg of prednisolone equivalent/day for  $\geq$ 7 days are required for treatment of rash (and the participant does not intend to stop corticosteroids), JNJ-3989 needs to be permanently discontinued. NAs can be continued. If the rash is considered to be most likely due to concomitant illness or non-study interventions, standard management, including discontinuation of the likely causative agent, should be undertaken.

#### 8.3.6.2.7. Uveitis and Visual Complaints

Immune therapies have been uncommonly associated with visual complaints. Inflammation of components within the eye (eg, uveitis) is an uncommon, but clinically important, event. An ophthalmologist should evaluate visual complaints with examination of the conjunctiva, anterior and posterior chambers, and retina. Complaints of double vision should also prompt medical evaluation. In addition to ocular inflammatory events, a work-up should also consider pituitary inflammation as a cause. Refer to [Table 11](#) for the management of uveitis and visual complaints.

If systemic corticosteroids are required for treatment of rash uveitis and visual complaints, nivolumab need to be permanently discontinued.

**Table 11: Management of Uveitis and Visual Complaints**

| Grade     | Recommended Actions   |
|-----------|---|
| Grade 1-2 | Thorough eye examination
Topical corticosteroids should be considered
Persisting despite topical steroids, treat as Grade 3-4 |
| Grade 3-4 | Thorough eye examination
Systemic corticosteroids
Discontinue nivolumab   |

#### 8.3.6.2.8. Lipase/Amylase Elevations

Asymptomatic elevations in lipase and amylase have been reported in anti-PD-1 therapy studies in which systemic monitoring was used. Very few participants reported associated symptoms (eg, abdominal pain) or radiographic findings (eg, stranding) consistent with pancreatitis. Thus, there does not seem to be clinical significance to the elevated laboratory values. The recommended management of anti-PD-1 therapy-related elevated lipase/amylase values centers around close observation. Investigators should ensure that participants have no associated symptoms consistent with pancreatitis, such as abdominal pain. Serum lipase levels are evaluated at the timepoints listed in the [Schedule of Activities](#). If pancreatitis is suspected based on serum lipase level, amylase should be checked. Corticosteroids do not seem to alter the natural history of lipase/amylase elevations. Laboratory values tend to fluctuate on a day-to-day basis and eventually return to baseline or low-grade levels over the course of weeks, whether or not participants receive corticosteroids. Asymptomatic elevations should be monitored approximately weekly.

### 8.3.6.2.9. Infusion-related Reactions

Hypersensitivity reactions can occur with nivolumab treatment. Since nivolumab contains only human immunoglobulin protein sequences, it is less likely to induce a hypersensitivity reaction. However, if such a reaction were to occur, it might manifest with fever, chills, rigors, headache, rash, pruritis, arthralgias, hypo- or hypertension, bronchospasm, or other symptoms. Management of IRRs is provided in [Table 12](#). Investigators should follow their institutional treatment guidelines if acute allergic reaction or anaphylaxis occurs. For management of acute systemic allergic reactions during JNJ-3989 administration, refer to [Table 13](#).

All Grade 3 or 4 IRRs (refer to [Appendix 8: DAIDS Table with Modifications](#)) should be reported within 24 hours to the sponsor's Medical Monitor and reported as an SAE if criteria are met.

**Table 12: Management of Infusion-related Reactions**

| Grade     | Recommended Actions   |
|-----------|---|
| Grade 1   | No intervention indicated; remain at bedside and monitor participant until recovery from symptoms. Consider diphenhydramine 50 mg (or equivalent) and/or paracetamol 325 to 1000 mg (acetaminophen) at least 30 minutes.  |
| Grade 2   | Stop infusion; start IV saline infusion; give diphenhydramine 50 mg (or equivalent) IV and/or paracetamol 325 to 1000 mg (acetaminophen); consider corticosteroids and bronchodilator therapy; remain at bedside and monitor participant until recovery from symptoms. If systemic corticosteroids are used for treatment of Grade 2 IRRs, nivolumab needs to be permanently discontinued.
Restart infusion at 50% of initial rate (only if no systemic corticosteroids were administered): if no further complications ensue after 30 minutes, the rate may be increased to 100% of the original infusion rate; monitor participant closely.
Symptoms recur: stop and discontinue further treatment at that visit; administer diphenhydramine 50 mg IV, and remain at bedside and monitor the participant until resolution of symptoms. The amount of study drug infused must be recorded in the CRF. |
| Grade 3-4 | Stop infusion; start IV saline infusion; recommend bronchodilators, epinephrine 0.2 to 1 mg of a 1:1,000 solution for subcutaneous administration or 0.1 to 0.25 mg of a 1:10,000 solution injected slowly for IV administration, and/or diphenhydramine 50 mg IV with methylprednisolone 100 mg IV (or equivalent), as needed.
Participant should be monitored until the investigator is comfortable that the symptoms will not recur. Nivolumab will be permanently discontinued. Investigators should follow their institutional guidelines for the treatment of anaphylaxis. Remain at bedside and monitor participant until recovery from symptoms. In the case of late-occurring hypersensitivity symptoms (eg, appearance of a localized or generalized pruritis within 1 week after treatment), symptomatic treatment may be given (eg, oral antihistamine, or corticosteroids).                                |

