- j. Liver disease staging assessments will be performed based on Fibroscan or liver biopsy results, obtained within 6 months prior to screening or at the time of screening (in case of Fibroscan) or within 1 year prior to screening (in case of liver biopsy).
- k. Participants must have absence of signs of cirrhosis or portal hypertension (absence of nodules, smooth liver contour, normal portal vein, spleen size <12 cm) and absence of signs of HCC or clinically relevant renal abnormalities on an abdominal ultrasound performed within 3 months prior to screening or at the time of screening. In case of suspicious findings on conventional ultrasound the participant may still be eligible if HCC or clinically relevant renal abnormalities have been ruled out by a more specific imaging procedure (contrast-enhanced ultrasound, CT or MRI).
- l. When both JNJ-3989 and nivolumab are administered at the same visit, JNJ-3989 should be administered first (preferably in abdomen) followed within approximately 30 minutes by IV infusion of nivolumab. No JNJ-3989/nivolumab will be administered or dispensed during follow-up.
- m. Before each administration of study intervention, the participant will be evaluated for possible toxicities that may have occurred since the previous dose of study intervention. The most recent laboratory results and general physical status must be reviewed. If immune-related toxicity has occurred, the criteria outlined in Section 8.3.6 must be followed for management.
- n. NA prescription should follow the standard of care. In between study visits, participants will take NA at home and will bring their NA with them to each study visit. At study visits, the NA should be taken on site. Compliance will be assessed by the investigator based on participant interview.
- o. Prior to starting nivolumab treatment, the participant's most recent ALT value (tested by local or central lab) should be <3x ULN with no change in autoimmune status. In case the injection of nivolumab would not be in the interest of the participant, this should be discussed with the sponsor.
- p. Complete physical examination, including height (only at screening), body weight, skin and other body systems examination.
- q. Vital signs include supine SBP, DBP, pulse rate, and body temperature. Vital signs should preferably be assessed prior to any blood sampling.

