- Nivolumab: 0.3 mg/kg, one single IV infusion at Week 16 for Arm 1 or 3 IV infusions at Weeks 16, 20, and 24 for Arm 2.

Assessments and sampling will be done for efficacy (eg, HBsAg, HBeAg, and HBV DNA), safety (eg, [S]AEs, irAEs, laboratory evaluations, ECGs, vital signs, physical examinations), PK, PK/PD, viral genome sequencing, PBMC, human leukocyte antigen (HLA) typing, immunogenicity and pharmacogenomics, and for exploratory analysis of host and viral markers.

The total duration of individual participation will be up to 72 weeks (screening not included). Participants will be considered to have completed the study if they have completed all the assessments of the final study visit (ie, FU Week 48).

If a participant prematurely discontinues treatment with JNJ-3989 before Week 24, the participant will also discontinue further treatment with nivolumab and will have an early withdrawal (WD) visit. Follow-up assessments should be obtained as per the [Schedule of Activities](#) until 48 weeks after the end of JNJ-3989 treatment, unless the participant withdraws consent. The NA treatment will be continued until the end of the study.

If a participant prematurely discontinues nivolumab, treatment with JNJ-3989 and NA should be continued as planned, unless a treatment discontinuation rule for JNJ-3989 is also met. In that case, JNJ-3989 will also be discontinued but NA treatment should be continued as planned.

If a participant withdraws prematurely from the study, the reason for withdrawal (if known) should be documented. Participants who withdraw consent will be offered an optional safety follow-up visit to occur on the day of consent withdrawal.

An internal DRC will be commissioned for monitoring safety of participants enrolled in this study. In addition, an IFLEP will be appointed. Refer to Committees Structure in [Appendix 3: Regulatory, Ethical, and Study Oversight Considerations](#) for details.

A diagram of the study design is provided in Section 1.2, Schema.

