### 7.1.1. Discontinuation of JNJ-3989

Treatment with JNJ-3989 must be discontinued if any of the following occurs:

- The participant withdraws consent to receive study intervention.
- The investigator believes that for safety reasons or tolerability reasons (eg, AE) it is in the best interest of the participant to discontinue JNJ-3989.
- The participant becomes pregnant.
- The participant has  $\geq$ Grade 3 rash (see Section 10.6, Appendix 6: Rash Management).
- The participant has  $\geq$ Grade 3 allergic reaction or worsening of Grade 2 allergic reaction (see Section 8.3.6.4.1, Acute Systemic Allergic Reactions).
- The participant has signs of hepatic decompensation (ie, clinical evidence of ascites, bleeding varices, or hepatic encephalopathy) or an increase in direct bilirubin  $>1.5x$  ULN in combination with INR  $\geq 1.5x$  ULN or albumin  $<3.0$  g/dL. Alternative treatment options (outside the study) should be considered in consultation with the sponsor.
- The participant has treatment-emergent ALT/AST elevations, as described in Section 8.3.6.1, Intervention-emergent ALT/AST Elevations including immune-related hepatic AEs.
- The participant has a confirmed  $\geq$ Grade 3 eGFR abnormality and a drop from baseline of  $>10$  mL/min/1.73 m^2, based on creatinine (calculated by the CKD-EPI formula), that persists despite changing tenofovir disoproxil to ETV or TAF (if the participant was receiving tenofovir disoproxil) and that is considered at least possibly related to JNJ-3989.
- The participant has a QTcF prolongation (defined as a QTcF value of  $>500$  ms, or an increase from baseline of  $>60$  ms) at any given time point.
- The participant requires  $\geq 7$  days of treatment with any of the disallowed medications listed in Section 6.5, Concomitant Therapy, and does not intend to discontinue treatment with the disallowed medication.
- The participant has confirmed HBV virologic breakthrough (ie, confirmed on-treatment HBV DNA increase by  $>1$  log10 IU/mL from nadir or confirmed on-treatment HBV DNA level  $>200$  IU/mL in participants who had HBV DNA level  $<$ LLOQ of the HBV DNA assay). If virologic breakthrough occurs during nivolumab administration, this does not automatically lead to stop of JNJ-3989 and/or nivolumab, but should be assessed/discussed with the sponsor.

In case of virologic breakthrough, a viral sequencing sample may be collected at the next visit.

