### 8.3.6.4. Other Adverse Events

#### 8.3.6.4.1. Acute Systemic Allergic Reactions

Table 13: Management of Acute Systemic Allergic Reactions

| Grade  | Recommended Actions  |
|--|--|
| Grade 1 (Localized Urticaria [Wheals] With no Medical Intervention Indicated)   | Participants may continue study intervention. Cetirizine, levocetirizine, topical corticosteroids or antipruritic agents may be prescribed. Participants should be advised to contact the investigator immediately if there is any worsening of the acute systemic allergic reaction.  |
| Grade 2 (Localized Urticaria With Intervention Indicated, or Mild Angioedema With no Intervention Indicated)  | Participants may continue study intervention. Cetirizine, levocetirizine, topical corticosteroids or antipruritic agents may be prescribed. Participants should be advised to contact the investigator immediately if there is any worsening of the acute systemic allergic reaction, in which case the participant will permanently discontinue JNJ-3989 (and nivolumab if applicable). Rechallenge is not allowed. |
| Grade 3 (Generalized Urticaria, Angioedema With Intervention Indicated, or Symptoms of Mild Bronchospasm) and Grade 4 (Acute Anaphylaxis, Life-threatening Bronchospasm, or Laryngeal Edema) | Participants will permanently discontinue JNJ-3989 (and nivolumab if applicable). Rechallenge is not allowed. Participants will be treated as clinically appropriate. Participants should be followed until resolution of the AE and standard management should be undertaken.   |

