| Vertigo   | Vertigo causing no or
minimal interference
with usual social &
functional activities   | Vertigo causing greater
than minimal
interference with usual
social & functional
activities                                 | Vertigo causing
inability to perform
usual social &
functional activities  | Disabling vertigo
causing inability to
perform basic self-care
functions   |
| Visual Changes
(assessed from
baseline)                                 | Visual changes
causing no or minimal
interference with usual
social & functional
activities                                 | Visual changes causing
greater than minimal
interference with usual
social & functional
activities                          | Visual changes
causing inability to
perform usual social &
functional activities   | Disabling visual loss in
affected eye(s)   |

dB: decibel; kHz: kilohertz; NAP: not applicable

| SYSTEMIC  |  |   |  |  |
|---|--|---|--|--|
| PARAMETER   | GRADE 1
MILD  | GRADE 2
MODERATE   | GRADE 3
SEVERE  | GRADE 4
POTENTIALLY
LIFE-
THREATENING   |
| Acute Allergic Reaction  | Localized urticaria (wheals) with no medical intervention indicated                    | Localized urticaria with intervention indicated OR Mild angioedema with no intervention indicated   | Generalized urticaria OR Angioedema with intervention indicated OR Symptoms of mild bronchospasm | Acute anaphylaxis OR Life-threatening bronchospasm OR Laryngeal edema                                |
| Chills   | Symptoms causing no or minimal interference with usual social & functional activities  | Symptoms causing greater than minimal interference with usual social & functional activities  | Symptoms causing inability to perform usual social & functional activities                       | NAP  |
| Cytokine Release Syndromeh  | Mild signs and symptoms AND Therapy (ie, antibody infusion) interruption not indicated | Therapy (ie, antibody infusion) interruption indicated AND Responds promptly to symptomatic treatment OR Prophylactic medications indicated for $\leq 24$ hours | Prolonged severe signs and symptoms OR Recurrence of symptoms following initial improvement      | Life-threatening consequences (eg, requiring pressor or ventilator support)                          |

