## **D)** Intercurrent events:

- Treatment discontinuation prior to Week 24: if the participant discontinued treatment prior to Week 24 then s/he will be considered non-responder (composite strategy).
- Major protocol deviations affecting efficacy: Table 9 identifies the deviations considered intercurrent event. Participants with such deviations and who have missing data for the endpoint will be considered as non-responders (composite strategy). For all other deviations not considered intercurrent events, the data are used regardless of the occurrence of major protocol deviations (treatment policy strategy).

- Deaths prior to FU Week 24 are handled in a composite strategy as participants who die prior to FU Week 24 will be considered as non-responders.
- **E)** Population-level summary:
  - **a. Primary (comparison vs fixed external proportion):** Difference in proportion of participants with HBsAg seroclearance at FU Week 24 using a fixed external proportion of 1%.
  - **b.** Secondary (comparison amongst regimens): Difference in proportion of participants with HBsAg seroclearance at FU Week 24 between study intervention arms.

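### The protocol does not settle whether a hypersensitivity reaction at a visit with both agents is an infusion reaction or an allergic reaction that also stops JNJ-3989

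*Protocol*

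**What the plan says.** **Timing.** Protocol Section 1.3.1 (footnote l) and Section 6.1 fix the order at shared visits: "JNJ-3989 should be administered first (preferably in abdomen) followed within approximately 30 minutes by IV infusion of nivolumab". Section 4.1 schedules nivolumab as "one single IV infusion at Week 16 for Arm 1 or 3 IV infusions at Weeks 16, 20, and 24 for Arm 2". JNJ-3989 is due at each of those visits.

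**Infusion-reaction route.** Section 8.3.6.2.9 describes a nivolumab hypersensitivity reaction and says "it might manifest with fever, chills, rigors, headache, rash, pruritis, arthralgias, hypo- or hypertension, bronchospasm, or other symptoms". It takes the grades from Appendix 8 and the management from Table 12. At Grade 2, Table 12 stops the infusion, lists bronchodilators among the options, and then allows: "Restart infusion at 50% of initial rate (only if no systemic corticosteroids were administered". At Grade 3-4 it stops nivolumab permanently and does not mention JNJ-3989. Section 7.1.2 lists a Grade 3 or 4 infusion-related reaction as a reason to stop nivolumab.

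**Allergic-reaction route.** Appendix 8 defines a Grade 3 acute allergic reaction as "Generalized urticaria OR Angioedema with intervention indicated OR Symptoms of mild bronchospasm". From Grade 3 upwards, Section 7.1.1 requires JNJ-3989 to stop; its criterion reads "Grade 3 allergic reaction or worsening of Grade 2 allergic reaction (see Section 8.3.6.4.1, Acute Systemic Allergic Reactions". Table 13 states for Grades 3 and 4: "Participants will permanently discontinue JNJ-3989 (and nivolumab if applicable). Rechallenge is not allowed". Section 7.1.2 also stops nivolumab whenever any Section 7.1.1 criterion is met.

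**Link to the analysis.** SAP Section 5.3.2, under intercurrent events: "if the participant discontinued treatment prior to Week 24 then s/he will be considered non-responder (composite strategy".

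**The concern.** Bronchospasm or generalized urticaria that begins during the infusion, shortly after the JNJ-3989 injection, fits both routes. One site could treat it as a Grade 2 infusion reaction, restart nivolumab and continue JNJ-3989. Another could record a Grade 3 allergic reaction and stop both agents for good. Participants with the same reaction would then be managed differently, in an area where the protocol intends a firm stopping rule. The choice of label could also settle primary response status, because stopping treatment before Week 24 counts as failure whatever the HBsAg level.

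**Working it through.** **1. The two routes side by side**

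| Event | As infusion reaction | As allergic reaction |
|---|---|---|
| Mild bronchospasm or generalized urticaria, settles promptly, no systemic steroids | If graded 2: Table 12 permits a restart at half rate; JNJ-3989 not mentioned | Grade 3 in Appendix 8: Section 7.1.1 and Table 13 stop both agents |
| Reaction agreed to be Grade 3 or 4 | Table 12 and Section 7.1.2 stop nivolumab; under Section 7.1 JNJ-3989 continues unless one of its own rules is met | Section 7.1.1 stops JNJ-3989, with no limit on the causal agent; Section 7.1.2 then stops nivolumab |

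Continuing JNJ-3989 in the middle column follows from Section 7.1 and from Table 12's silence. Table 12 does not state it.

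**2. Does Appendix 8 settle the grade?** It has no row for infusion-related reactions. Several rows partly overlap:
- Cytokine Release Syndrome gives Grade 2 to a reaction that needs the infusion interrupted and responds promptly.
- Acute Bronchospasm (respiratory table) gives Grade 2 to symptoms that need intervention.
- Acute Allergic Reaction gives Grade 3 to symptoms of mild bronchospasm.

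The functional table for unlisted events can always supply a grade. It does not say which term applies.

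**3. Do other sections settle precedence?**
- Section 8.3.6.2 refers to Section 7.1 for stopping rules, and Section 7.1 is mandatory. It therefore outranks the recommended actions in Table 12.
- Appendix 8 tells sites to take the higher grade when two are possible. This points away from the Grade 2 restart.
- Neither says whether a reaction attributed to nivolumab is an allergic reaction under Section 7.1.1. Section 7.1.2 lists the Grade 3-4 infusion reaction as a separate, nivolumab-only stop, which suggests that the two events are meant to differ. Section 7.1.1 draws no such distinction.

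**4. Relevance to the primary endpoint**

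Inputs: 18 participants in Arm 1 and 19 in Arm 2 (SAP Section 3); exact binomial test against 1%, one-sided 0.05, Hochberg over two arms (SAP Sections 5.1.7 and 5.3.4).

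The plan's own power figures come first. The planned differences of 15 and 20 points above 1% give rates of 16% and 21%. With rejection at two or more responders, power is 1 − (1−p)^n − np(1−p)^(n−1):
- n = 20, p = 0.16: 0.853 (stated: at least 85%)
- n = 16, p = 0.16: 0.751 (stated: at least 75%)

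Both reproduce; at p = 0.21 the values are 0.943 and 0.879.

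The p-values against 1% are:
- One responder, 1 − 0.99^n: 0.1655 (n = 18) and 0.1738 (n = 19).
- Two responders, 1 − 0.99^n − n(0.01)(0.99)^(n−1): 0.0138 (n = 18) and 0.0153 (n = 19).

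Two responders pass both Hochberg levels (0.05 and 0.025) and one passes neither. One responder rescored as a failure therefore reverses an arm's result only if that arm has exactly two.

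The documents give no reaction frequency. As an assumption, suppose one or two participants per arm are forced to non-response and the others respond at 16%:

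| Forced to non-response | Power, Arm 1 (n = 18) | Power, Arm 2 (n = 19) |
|---|---|---|
| 0 | 0.808 | 0.832 |
| 1 | 0.781 | 0.808 |
| 2 | 0.751 | 0.781 |

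The rule can act only at Week 16 (both arms) and Week 20 (Arm 2). At Week 24 the last JNJ-3989 dose is already in when the infusion starts. The schedule allows at most 18×1 + 19×3 = 75 infusions, of which 18 + 19×2 = 56 fall before Week 24.

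**The case against.** The strongest reply is that the rules are cumulative. Section 7.1 is mandatory, Table 12 only recommends, and JNJ-3989 continues after a nivolumab stop only if no JNJ-3989 rule is met. On that reading a Grade 3 allergic reaction stops both agents whatever Table 12 says, and the higher-grade instruction prevents a restart. This largely answers the restart half of the point. It does not answer the other half, because it presupposes that the event has been classed as allergic.

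A second reply is that Section 8.3.6.2.9 does separate the tables: it sends reactions during JNJ-3989 administration to Table 13 and infusion reactions to Table 12. A reader might infer that this separation is unusable because the agents are given so close together. That goes too far. The injection and the infusion are distinct administrations, and onset during one of them can often be placed. The separation is only partial, since a reaction shortly after both is not covered and Section 7.1.1 carries no such limit. Section 8.3.6.2.9 also refers acute allergic reactions to institutional guidelines, but that concerns treatment of the reaction and leaves the stopping rule in place. The Master Protocol's attribution and severity definitions, which the protocol adopts by reference, might narrow the gap; they are not among the documents reviewed.

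Third, the endpoint effect may be small. Section 8.3.6.2.9 calls hypersensitivity less likely with nivolumab, and the earlier low-dose nivolumab study described in Section 2.1 had no Grade 3 or 4 adverse events. This stands.

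**Conclusion.** The conflict is real but limited. What remains open is what happens to JNJ-3989 after a hypersensitivity reaction at a visit where both agents are given, and where the infusion-reaction grade comes from. The restart conflict is mostly answered by Section 7.1 and the higher-grade instruction, although Table 12 does not reflect either. The point should be corrected because it concerns a safety stopping rule, even though its frequency is unknown.

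Three stronger inferences are not supported:
- **That the primary result depends on the table a site uses.** This needs a qualifying reaction before Week 24, in a participant who would otherwise respond, in an arm with exactly two responders. Any other single reclassification would have the same effect there.
- **That 75 infusions, or 56 before Week 24, were exposed.** These are planned maxima. The SAP version history records that nivolumab dosing was halted on 20 June 2023, and the number actually given is not stated.
- **That only the allergic route leads to non-response.** SAP Section 5.3.2 does not say which agent's discontinuation counts. Stopping both meets any reading, but stopping nivolumab alone might also count.

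The verdict assumes that the Master Protocol does not define the two reaction types in a way that separates them.

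**What to change.** Reconcile Table 12, Table 13, Sections 7.1.1 and 7.1.2 and Appendix 8 so that:
- infusion-related reactions have a stated grading source, either a row in Appendix 8 or criteria written into Table 12;
- the table that governs a reaction at a visit where both agents are given is named;
- Section 7.1.1 states whether a reaction attributed to nivolumab meets its allergic-reaction criterion.

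The clinical team decides which rule applies; this review proposes none. SAP Section 5.3.2 should state which agent's discontinuation is the intercurrent event. Reactions that occurred before the nivolumab halt should be classified in one consistent way for that rule.

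The cost is wording in two tables, the stopping criteria, one appendix entry and one SAP sentence. No procedure or data collection is added.
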